16.1. Statistical Design (To Be Evaluated Independently in Each Arm)

In a phase II study conducted at Mayo Clinic including 27 myelofibrosis patients treated with single agent Lenalidomide, 37% of patients responded in terms of anemia or splenomegaly. In a similar study conducted at M.D. Anderson Cancer Center, a response rate of 24% in terms of anemia or splenomegaly was seen in 41 myelofibrosis patients also treated with single agent lenalidomide (Tefferi et al. 2006). A response rate similar to or better than Lenalidomide would be of interest for myelofibrosis patients treated with single agent Imetelstat. Although this study also includes response in terms of platelets or ANC, we would expect the majority of these patients to also have a response in terms of anemia or splenomegaly. In addition, we would expect patients with MDS/MPN or MDS with spliceosome mutations or ring sideroblasts to show similar outcomes to myelofibrosis. Therefore, an overall response rate of 30% would be considered early evidence of promising activity, for Arms A, B, C, E, F, and G. For Arm D, 20% response rate would be considered promising based on our single institutional experience of 91

patients with blast phase MF (Mesa et al. 2005); in the particular study, induction chemotherapy resulted in 0% CR and short-lived reversal to chronic phase disease in 41%.

Arms A, B, C, D, and G: The largest success proportion where the proposed treatment regimen would be considered ineffective in this population is 10%, and the smallest success proportion that would warrant subsequent studies with the proposed regimen in this patient population is 30%. The following two-stage Simon optimum design ([Simon 1989](#)) uses 11 or 26 patients to test the null hypothesis that the true success proportion in a given patient population is at most 10%.

16.2111 Stage 1: Enter 11 patients into each arm of the study (i.e. 11 patients each in Arms A, B, C, D, and G). If 0 or 1 successes are observed in the first 11 evaluable patients for each arm of the study, we will consider the regimen ineffective and terminate the particular arm of the study. Otherwise, if the number of successes is at least 2, we will proceed to Stage 2.

Stage 2: Enter an additional 15 patients into each arm of the study. If 4 or fewer successes are observed in the first 26 evaluable patients, considering each arm of the study separately, we will consider this regimen ineffective as it applies to the particular arm of the study. If 5 or more successes are observed in the first 26 evaluable patients, we may recommend further testing of this regimen in subsequent studies in this population.

Power and Significance Level: Assuming that the number of successes is binomially distributed, with a significance level of 9%, the probability of declaring that the regimen warrants further studies (i.e., statistical power) under various success proportions and the probability of stopping accrual after the first stage can be tabulated as a function of the true success proportion as shown in the table below.

If the true success proportion is...	0.10	0.15	0.20	0.25	0.30
Then the probability of declaring that the regimen is promising and warrants further study is...	0.09	0.28	0.52	0.72	0.85
And the probability of stopping after the first stage is...	0.70	0.49	0.32	0.20	0.11

As of Addendum 3, accrual to Arm C will be permanently discontinued due to preliminary evidence showing difference in outcome based on presence vs. absence of spliceosome mutations. The 11 patients slotted to enroll on Arm C will now be treated per the Arm A or Arm B dose schedule and then Arms A and B will permanently close. A total of 34 patients will be accrued between Arms A, B, and C. Due to incomplete accrual in these arms, the 33 evaluable patients that have been accrued to these arms will be combined and reported together as a pilot study. Since this group will not have a formal statistical design, the reporting of results in this group will be primarily descriptive in nature.

Arms E and F: The largest success proportion where the proposed treatment regimen would be considered ineffective in this population is 10%, and the smallest success proportion that would warrant subsequent studies with the proposed regimen in this patient population is 30%. The

following one-stage binomial design uses 25 patients to test the null hypothesis that the true success proportion in a given patient population is at most 10%.

Final Decision Rule: If 4 or fewer successes are observed in the first 25 evaluable patients, we will consider this regimen ineffective in this patient population. If 5 or more successes are observed in the first 25 evaluable patients, we may recommend further testing of this regimen in subsequent studies in this population.

Power and Significance Level: Assuming that the number of successes is binomially distributed, with a significance level of 10%, the probability of declaring that the regimen warrants further studies (i.e., statistical power) under various success proportions can be tabulated as a function of the true success proportion as shown in the table below.

If the true success proportion is...	0.10	0.15	0.20	0.25	0.30
Then the probability of declaring that the regimen is promising and warrants further study is...	0.10	0.32	0.58	0.79	0.91

Over Accrual: If more than the target number of patients are accrued, the additional patients will not be used to evaluate the stopping rule or used in any decision making process. Analyses involving over accrued patients are discussed in Section [16.6](#).

Sample Size: As of Addendum 3, accrual to Arm C will be permanently discontinued. The 11 patients slotted to enroll on Arm C will now be treated per the Arm A or Arm B dose schedule. A total of 34 patients will be accrued between Arms A, B, and C. Accrual will continue per protocol in Arm D and three additional arms (Arms E, F, and G) will be added. A total of 26 evaluable patients (Arms D and G) or 25 evaluable patients (Arms E and F) will be accrued in each of the remaining arms. An additional 3 patients will be accrued in each arm to account for patients who need to be replaced. Therefore, the maximum overall sample size across all arms of the study is now 148 patients.

As of 22Jan2014 study is closed to enrollment with a total of 80 patients enrolled.

Accrual Rate and Study Duration: As of 22Jan2014, all arms have permanently discontinued accrual. The 11 patients slotted to enroll on Arm C will now be treated per the Arm A or Arm B dose schedule.

Other considerations: Adverse events, quality/duration of response, and patterns of treatment failure observed in this study, as well as scientific discoveries or changes in standard care will be taken into account in any decision to terminate the study

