16. STATISTICAL CONSIDERATIONS AND METHODOLOGY

Overview: This protocol will assess the efficacy of different schedules of imetelstat in six cohorts of patients with myelofibrosis (including blast-phase disease in Arm D) and one cohort of patients with MDS/MPN or MDS with spliceosome mutations or ring sideroblasts using a phase II study design in each arm independently.

Descriptive statistics will be used to summarize baseline patient characteristics, treatment administration, efficacy, and safety outcomes. Descriptive summaries of discrete data will present the number of patients and the incidence as a frequency and as a percentage. Descriptive summaries of continuous data will present the group mean, standard deviation, median, minimum, maximum, and sample size.

For regulatory reporting purposes, there are two time points for the analyses: (1) the primary analysis 48 weeks after the last patient has been enrolled, and (2) the final analysis after all patients have completed the study. A separate and detailed statistical analysis plan (SAP) developed prior to primary analysis will supersede analyses specified in the protocol. Deviations from the SAP will be noted in the final study report.

Primary Endpoint: The primary endpoint in each arm of this trial is overall response rate. Overall response will be defined as a CI, PR, or CR (for Arms A, B, C, E, and F) according to the IWG-MRT consensus criteria for MF, or as a HI, PR or CR (for Arm G) according to the IWG consensus criteria for MDS, or the achievement of <5% peripheral blood and bone marrow blast % that lasts for at least two months (for Arm D).

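### Protocol 16.1 calls a 20% response rate promising for Arm D but designs the arm around 30%; at 20% the planned power is 0.52, not 0.85

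*Protocol*

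**What the plan says.** Protocol 16.1 sets 30% as early evidence of promising activity for Arms A, B, C, E, F and G. Arm D is left out of that list and given a separate figure with a disease-specific basis: "For Arm D, 20% response rate would be considered promising based on our single institutional experience of 91" patients with blast-phase disease.

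The following paragraph, headed for Arms A, B, C, D and G, sets one two-stage design for all five. The null is a true response rate of at most 10%, and "the smallest success proportion that would warrant subsequent studies with the proposed regimen in this patient population is 30" per cent. Stage 1 stops on 0 or 1 success in 11. At 26 patients, 4 or fewer successes means ineffective and 5 or more permits a recommendation for further testing. The accompanying table gives the probability of declaring the regimen promising as 0.09, 0.28, 0.52, 0.72 and 0.85 at true rates of 0.10, 0.15, 0.20, 0.25 and 0.30. The probability of stopping after stage 1 is 0.70, 0.49, 0.32, 0.20 and 0.11.

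SAP 1.3 repeats the 26 evaluable patients for Arm D and gives no target rate. SAP 4.2.2 reports response rates by arm with exact 95% confidence intervals.

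For the secondary note: Arms E and F use a single-stage rule, "If 4 or fewer successes are observed in the first 25 evaluable patients, we will consider this regimen ineffective in this patient population", with stated power of 0.91 at 30%. On accrual, "As of 22Jan2014 study is closed to enrollment with a total of 80 patients enrolled", against a maximum of 148.

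**The concern.** The two Arm D sentences give different answers to one question: what true response rate should the arm be able to detect? The first says 20% and gives a reason particular to blast-phase disease. The second says that nothing below 30% would warrant further study. No 20% design for Arm D appears anywhere, and the 0.20 column of the table is not identified as Arm D's power at its own benchmark.

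What is at stake is how a negative Arm D result is read. Someone who takes 20% from the rationale and 0.85 from the end of the power table would think the arm well powered for the rate of interest. Under the planned rule, a regimen with a true 20% rate would be called ineffective almost half the time.

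**Working it through.** **Inputs** (all Protocol 16.1): null 10%; design alternative 30%; Arm D promising rate 20%; stage 1 continues if X1 ≥ 2 of 11; final success if the total is ≥ 5 of 26 (15 more patients in stage 2).

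**Formulas** (exact binomial):
- P(stop at stage 1) = P(Bin(11, p) ≤ 1)
- P(declare promising) = Σ over x = 2 to 11 of P(Bin(11, p) = x) × P(Bin(15, p) ≥ 5 − x)

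**Reproducing the protocol's table**

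| True rate | Promising: stated | Recomputed | Stage-1 stop: stated | Recomputed |
|---|---|---|---|---|
| 0.10 | 0.09 | 0.0865 | 0.70 | 0.6974 |
| 0.15 | 0.28 | 0.2816 | 0.49 | 0.4922 |
| 0.20 | 0.52 | 0.5194 | 0.32 | 0.3221 |
| 0.25 | 0.72 | 0.7190 | 0.20 | 0.1971 |
| 0.30 | 0.85 | 0.8516 | 0.11 | 0.1130 |

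Every entry agrees after rounding.

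**Arm D at its 20% benchmark**
- Stage-1 stop: 0.8^11 + 11 × 0.2 × 0.8^10 = 0.0859 + 0.2362 = 0.3221.
- Promising, by stage-1 count: x = 2, 0.2953 × 0.6020 = 0.1778; x = 3, 0.2215 × 0.8329 = 0.1844; x = 4, 0.1107 × 0.9648 = 0.1068; x ≥ 5, 0.0504. The sum is 0.5194.
- Fail at stage 2: 1 − 0.5194 − 0.3221 = 0.1584 (from unrounded values).
- Total chance of being called ineffective: 0.3221 + 0.1584 = 0.48.

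**Can a failing result exclude 20%?** The upper exact 95% limit is the 0.975 quantile of Beta(x + 1, n − x). The planned design can fail in only five ways:

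| Outcome | Upper 95% limit |
|---|---|
| 0/11 | 28.5% |
| 1/11 | 41.3% |
| 2/26 | 25.1% |
| 3/26 | 30.2% |
| 4/26 | 34.9% |

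All exceed 20%.

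**Secondary note, Arms E and F.** P(Bin(25, 0.30) ≥ 5) = 0.9095, matching the stated 0.91. Protocol 16.1 puts 34 patients, 33 of them evaluable, in Arms A–C. That leaves 80 − 34 = 46 or 80 − 33 = 47 for Arms D to G together. E and F alone need 25 + 25 = 50, so at least one of them fell short even if D and G had enrolled nobody.

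**The case against.** The strongest reply is that Arm D's operative rule is not in doubt. The null and both cut-offs are explicit, and neither 20% nor 30% is a pass mark. The final cut-off, 5/26, is an observed 19.2%, so the 20% might have been meant as an observed rate. The consequence is also printed already: 0.52 and 0.32 stand in the 0.20 column under a heading that names Arm D. The exact intervals in SAP 4.2.2 would show that a failing result is compatible with 20%. Accrual is closed and the SAP contains no go/no-go test.

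Most of this stands, and it is why the point is minor. It does not remove the contradiction. The parallel 30% for the other arms is the design's true-rate alternative, and the table uses the word promising for true rates; an observed-rate meaning would have to be stated. Protocol 16 says that the SAP "will supersede analyses specified in the protocol", but not whether the protocol's verdict of ineffective lapses.

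A reader might infer more than the documents support:
- *That the table or rule is wrong, or the arm must be resized.* The table reproduces exactly and the rule is usable. For scale only, a single-stage test of 10% against 20% with type I error at most 0.09 and power at least 0.85 needs 70 patients (11 or more responses; 0.087 and 0.853). With enrolment closed, that is no remedy.
- *That Arm D was in fact wrongly judged.* The documents do not show how the arm ended.
- *That no negative conclusion is possible for an arm closed short.* A negative can already be fixed: 3 responses in 24 cannot become 5 in 25.
- *That separate reporting of Arms A and B in the SAP is a conflict of the same kind.* Protocol 16.1 says that those patients "will be combined and reported together as a pilot study". However, Protocol 1.4.1 ties the consolidation to meetings and publication, and Protocol 16 lets the SAP replace protocol analyses. That largely answers the point.

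**Conclusion.** The point holds as a minor inconsistency that is wrong as written. Arm D has two unreconciled targets, 20% and 30%. The 0.85 power belongs to the second; at the first it is 0.52, with 0.32 probability of stopping at stage 1 and about 0.48 of being called ineffective overall. The documents do not show which target was intended.

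The effect is on interpretation only. The figures assume the design is run as planned, with exactly 11 or 26 evaluable patients, independent binomial responses, and intervals of the type SAP 4.2.2 names. They describe the planned design, not the arm as it closed.

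The E and F note is secondary. The 0.91 is a correct planned figure for 25 evaluable patients, and the overall shortfall (80 against 148) is disclosed. What is missing is the evaluable number per arm and a statement that the 0.91 cannot apply to both arms. The documents do not say which arm fell short or by how much.

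**What to change.** In Protocol 16.1, reconcile the two Arm D sentences, keeping the 10% null and the 1/11, 4/26 rule, and carry the same statement into SAP 1.3.

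- If 20% is the rate of interest, state: *For Arm D the null is 10% and the rate of interest is 20%; the planned design has power 0.52 and a 0.32 probability of stopping at stage 1 at that rate, so failing the rule does not by itself rule out 20%.*
- If 30% was intended, correct the sentence that calls 20% promising for Arm D.

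In SAP 1.3, also give the evaluable number in each arm. State that the 0.91 power for Arms E and F assumes 25 evaluable patients each, which both arms cannot have reached.

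The cost is a few sentences, with no added patients, visits or analyses. If 20% is confirmed, the stated power for Arm D becomes less favourable.

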16.2. Analysis Plan

For regulatory reporting purposes, the primary analysis will commence 48 weeks after the last patient has been enrolled, and the final analysis after all patients have completed the study. Analysis of patients with blast-phase MF (Arm D) and those with MDS/MPN or MDS (Arm G) will be performed and presented separately.

16.3. Primary Outcome Analyses(to be evaluated in each arm independently)

Definition: The primary endpoint in each arm of this trial is the overall response rate. For Arms A, B, C, E, and F overall response is defined to be a CI, PR, or CR noted as the objective status according to the IWG-MRT consensus criteria for MF. Response in Arm G is defined as HI, PR or CR according to the IWG criteria for MDS ([Cheson et al. 2006](#)). Response in Arm D is defined by a durable (2 months or more) decrease in peripheral blood and bone marrow blast percentage to less than 5%. All patients meeting the eligibility criteria who have signed a consent form and have begun treatment will be evaluable for overall response.

Estimation: The proportion of successes will be estimated in each arm by the number of successes divided by the total number of evaluable patients. Ninety-five percent Clopper-Pearson exact binomial confidence intervals for the true success proportion will be calculated.

16.4. Secondary Outcome Analyses (to Be Evaluated in Each Arm Independently)

16.4.1. Adverse Events

All eligible patients that have initiated treatment will be considered evaluable for assessing adverse event rate(s). The maximum grade for each type of adverse event will be recorded for each patient, and frequency tables will be reviewed to determine patterns. Additionally, the relationship of the adverse event(s) to the study treatment will be taken into consideration.

16.4.2. Spleen Response

Spleen response is defined as either a minimum 50% reduction in palpable splenomegaly of a spleen that is at least 10 cm at baseline or a spleen that is palpable at less than 10 cm but more than 5 cm at baseline becomes not palpable. Spleen size will be measured by physical examination (palpable distance from the left costal margin) at baseline and as part of each response assessment. The proportion of patients achieving spleen response per the IMG-MRT criteria ([Section 11](#)) will be calculated by the number of patients who achieve spleen response divided by the total number of evaluable patients with spleen involvement at baseline (estimated to be approximately 80% of patients). Same method will be applied to splenectomized patients for assessment of hepatomegaly response. Ninety-five percent Clopper-Pearson exact binomial confidence intervals for the true proportion of patients with spleen response will be calculated.

16.4.3. Transfusion-Independence

Transfusion dependency is defined by a history of at least 2 units of red blood cell transfusions in the last month for a hemoglobin level of less than 85 g/L that was not associated with clinically overt bleeding (see IWG-MRT criteria; [Section 11](#)). The proportion of patients achieving transfusion independence during the first 9 cycles of treatment will be estimated by the number of patients who achieve transfusion independence divided by the total number of evaluable patients who were transfusion dependent at baseline. Ninety-five percent Clopper-Pearson exact

binomial confidence intervals for the true proportion of patients who become transfusion independent will be calculated. The same statistical method will be applied to anemia response for Arms A, B, E and F per IWG-MRT for myelofibrosis (Tefferi et al. 2013) and erythroid response for Arm G per IWG response criteria for MDS ([Cheson et al. 2006](#)).

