⁴ See table 15 for definitions of anemia response, spleen response and progressive disease. Increase in severity of anemia constitutes the occurrence of new transfusion dependency or a ≥ 20 g/L decrease in hemoglobin level from pre-treatment baseline that lasts for at least 12 weeks. Increase in severity of thrombocytopenia or neutropenia is defined as a 2-grade decline, from pre-treatment baseline, in platelet count or absolute neutrophil count, according to Common Terminology Criteria for Adverse Events (CTCAE) version 4.0. In addition, assignment to clinical improvement (CI) requires a minimum platelet count of $\geq 25,000 \times 10^9/L$ and absolute neutrophil count of $\geq 0.5 \times 10^9/L$.

⁵ Applicable only to patients with baseline hemoglobin of <100 g/L. In patients not meeting the strict criteria for transfusion-dependency at the time of study enrollment (see below), but have received transfusions within the previous month, the pre-transfusion hemoglobin level should be used as the baseline

⁶ Transfusion dependency before study enrollment is defined as transfusions of at least 6 units of packed red blood cells (PRBC), in the 12 weeks prior to study enrollment, for a hemoglobin level of <85 g/L, in the absence of bleeding or treatment-induced anemia. In addition, the most recent transfusion episode must have occurred in the 28 days prior to study enrollment. Response in transfusion dependent patients requires absence of any PRBC transfusions during any consecutive “rolling” 12-week interval during the treatment phase, capped by a hemoglobin level of ≥ 85 g/L.

⁷ In splenectomized patients, palpable hepatomegaly is substituted with the same measurement strategy

⁸ Confirmation of spleen or liver responses by imaging studies is recommended (but not required), where a $\geq 35\%$ reduction in spleen or liver volume, assessed by magnetic resonance imaging (MRI) or computed tomography (CT), is required for confirmation. Furthermore, a $\geq 35\%$ volume reduction in the spleen or liver, by MRI or CT, constitutes a response regardless of what is reported with physical examination.

Symptoms are evaluated by the Myeloproliferative Neoplasm Symptom Assessment Form total symptom score (MPN-SAF TSS). The MPN-SAF TSS is assessed by the patients themselves and includes fatigue, concentration,

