4.3. Major Secondary Endpoints

4.3.1. Definition

Spleen Response

Spleen response is defined as either a minimum 50% reduction in palpable splenomegaly of a spleen that is at least 10 cm at baseline or a spleen that is palpable at less than 10 cm but more than 5 cm at baseline becomes not palpable.

Transfusion Independence

Transfusion dependency is defined by a history of at least 2 units of red blood cell transfusions in the last month or a baseline hemoglobin level of less than 85 g/L that was not associated with clinically overt bleeding. For a transfusion dependent subject, transfusion independence is defined as he/she met either of the following conditions:

- Received no more than 1 unit of red blood cell transfusions in a rolling time interval of 30 days or more.
- Had a hemoglobin level increase over baseline more than 2g/dl if his/her baseline hemoglobin level was less than 85 g/L and received no transfusion.

Time to Response (TTR)

Time to response is defined as the duration from Study Day 1 to the earliest date that a response is first documented. For non-responders, it will be censored at the date of progressive disease/relapse or the date of the last adequate assessment, whichever comes first.

Duration of Response (DoR)

Duration of response is defined for responders as the interval from date of the initial documentation of a response to the date of first documented evidence of disease progression (or relapse for subjects who experience CR). For those subjects who are still without progression/relapse, DoR will be censored at the last adequate assessment.

Overall Survival (OS)

OS is defined as the interval from Study Day 1 to the date of death from any cause. Survival time of living subjects will be censored on the last date a subject is known to be alive or lost to follow-up.

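### Baseline transfusion dependence has three inconsistent definitions, and those in protocol 16.4.3 and SAP 4.3.1 are not the IWG-MRT criteria that the objective names

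*Protocol*

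**What the plan says.** **Objective.** Protocol 2.2 and SAP 1.1 both set transfusion independence in previously dependent patients as a secondary objective, judged by IWG-MRT criteria. The protocol points to Section 11 for them.

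**Dependence at baseline** is then defined three times:

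- Protocol 16.4.3: "Transfusion dependency is defined by a history of at least 2 units of red blood cell transfusions in the last month", given for hemoglobin below 85 g/L, without overt bleeding, with a cross-reference to Section 11. Appendix A has the same wording, as a DIPSS-plus prognostic factor.
- Protocol Table 15, footnote 6, in Section 11: "transfusions of at least 6 units of packed red blood cells (PRBC), in the 12 weeks prior to study enrollment", for hemoglobin below 85 g/L, without bleeding or treatment-induced anemia; also, "the most recent transfusion episode must have occurred in the 28 days prior to study enrollment".
- SAP 4.3.1: "at least 2 units of red blood cell transfusions in the last month or a baseline hemoglobin level of less than 85 g/L", without overt bleeding.

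**Independence afterwards** is defined twice. Footnote 6: "Response in transfusion dependent patients requires absence of any PRBC transfusions during any consecutive" rolling 12-week interval, ending with hemoglobin of at least 85 g/L. SAP 4.3.1 accepts either of two conditions. One is "Received no more than 1 unit of red blood cell transfusions in a rolling time interval of 30 days or more". The other is a hemoglobin rise above 2 g/dL from a baseline below 85 g/L with no transfusion.

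**Analysis.** Protocol 16.4.3 divides the number becoming independent in the first 9 cycles by the number dependent at baseline, with a 95% Clopper-Pearson interval. SAP 4.3.2 only lists each subject's status. Protocol Section 16 says that the SAP supersedes the protocol's analyses.

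**The concern.** The baseline rule decides who is in the denominator of the 16.4.3 proportion and whose status has meaning in the SAP listing. A window of one month can be satisfied by one recent transfusion episode; 6 units in 12 weeks requires sustained need. Patients with low or irregular need are the ones most likely to pass 12 weeks without transfusion whether or not the drug works, so admitting more of them can raise the apparent success rate.

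The definitions also split the endpoints. The anemia component of clinical improvement, and so the primary endpoint in the myelofibrosis arms other than Arm D, uses Table 15. A patient who falls short of footnote 6 needs a hemoglobin rise of at least 20 g/L there, while 16.4.3 may count the same patient as dependent and credit freedom from transfusion.

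**Working it through.** The documents give no expected rate, sample size or number of dependent patients for this endpoint, so there is no planned figure to reproduce.

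**1. The rules side by side.** Two units per 28 days sustained for 84 days is 2 × 84/28 = 6 units, so the two unit rules imply the same average intensity. They differ in the window. Four example patients, with transfusions given for hemoglobin below 85 g/L and a month taken as 28 days:

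| Patient | 16.4.3 | Footnote 6 | SAP 4.3.1 |
|---|---|---|---|
| 2 units every 28 days for 12 weeks | dependent | dependent | dependent |
| One 2-unit episode in the last month, nothing earlier | dependent | not | dependent |
| 5 units in weeks 1–8, then 1 unit in the last 28 days | not | dependent | only if baseline hemoglobin <85 g/L |
| Never transfused, baseline hemoglobin 80 g/L | not | not | dependent |

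The 16.4.3 and footnote 6 sets are not nested (rows 2 and 3). The patient in row 4 meets the SAP's first independence condition simply by remaining untransfused for 30 days.

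**2. Effect on a rate.** Assumptions, none from the documents: episodes follow a Poisson process at a constant rate per patient, and there is no drug effect. Nine cycles last 9 × 21 = 189 days (27 weeks) or 9 × 28 = 252 days (36 weeks). Success is a 12-week interval with no transfusion; the hemoglobin condition is ignored.

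For μ two-unit episodes per 28 days:

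- 2-unit rule: P = 1 − e^(−μ)
- 6-unit rule (at least 3 episodes in 84 days, at least 1 in the last 28): P = Pr[Pois(3μ) ≥ 3] − e^(−μ) × Pr[Pois(2μ) ≥ 3]

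At μ = 0.5 these are 0.393 and 0.191 − 0.607 × 0.080 = 0.142. The success columns are simulated.

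| μ | 2-unit rule | 6-unit rule | Chance success, 27 wk | 36 wk |
|---|---|---|---|---|
| 0.5 | 0.393 | 0.142 | 62% | 76% |
| 1 | 0.632 | 0.458 | 23% | 33% |
| 2 | 0.865 | 0.835 | 2% | 3% |

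At a fixed μ, transfusions after entry are independent of those before it, so the chance success is the same under either entry rule. A difference arises only when patients differ in μ. With the three rates equally common, the rate is Σ(entry × success)/Σ(entry):

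- 27 weeks, 2-unit rule: (0.393×0.62 + 0.632×0.23 + 0.865×0.02)/1.890 = 21.5%
- 27 weeks, 6-unit rule: (0.142×0.62 + 0.458×0.23 + 0.835×0.02)/1.435 = 14.6%; gap 6.9 points
- 36 weeks: 0.533/1.890 = 28.2% against 0.284/1.435 = 19.8%; gap 8.4 points

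A second simulated mix uses 0.5, 1, 1.5, 2, 3 and 4 units per 28 days, equally likely:

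| Episode size | Weeks | 2-unit rule | 6-unit rule | Gap |
|---|---|---|---|---|
| 2 units | 27 | 25.4% | 16.7% | 8.7 |
| 2 units | 36 | 32.1% | 21.8% | 10.3 |
| 1 unit | 27 | 5.1% | 2.1% | 3.0 |
| 1 unit | 36 | 7.2% | 3.1% | 4.1 |

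The three-rate mix (1, 2 and 4 units per 28 days) with 1-unit episodes at 27 weeks gives (0.26×0.22 + 0.59×0.02)/1.76 = 3.9% against (0.08×0.22 + 0.51×0.02)/1.56 = 1.8%, a gap of 2.1 points. If every patient needs 2 units per 28 days in 2-unit episodes, the rates at 27 weeks are 24% and 23%.

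**3. Under the SAP's own independence rule.** In the six-level mix with no drug effect, 91–98% of patients entering by the 2-unit rule and 89–97% of those entering by the 6-unit rule have some 30-day window with no more than 1 unit. The SAP's hemoglobin entry clause was not simulated.

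**The case against.** Four points on the other side carry weight.

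- **No rate in the superseding plan.** SAP 4.3.2 only lists status. This stands: the numerical effect applies to the 16.4.3 proportion or to a rate that someone derives from the listing. The listed status still rests on the baseline class.
- **The SAP's independence rule matters more than the entry rule.** This stands. With roughly nine in ten unchanged patients counted as independent under either entry rule, correcting entry alone would barely alter the SAP result.
- **Table 15 already handles the borderline patient.** Footnote 5 takes the pre-transfusion hemoglobin as baseline for patients short of strict dependency who were transfused in the previous month. That settles their anemia response. It does not settle who belongs in the 16.4.3 denominator.
- **Footnote 6 is a myelofibrosis criterion.** This stands: Arm G is assessed by the MDS criteria.

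A reader might infer that the 2-unit rule is shown to inflate the rate, perhaps by the 62% to 76% in the first row of the rate table. The documents do not support that. Those figures are identical under both entry rules, inflation needs unequal transfusion need, and the documents give no distribution of need. A reader might also infer that the SAP simply repeats 16.4.3; its hemoglobin alternative makes it a separate, wider definition.

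**Conclusion.** The inconsistency is certain and lies in current text. There are three definitions of dependence, and neither the one in 16.4.3 nor the one in the SAP is the IWG-MRT definition that both objectives name. The same patient can be classified differently for the secondary endpoint and for the anemia component of the primary endpoint.

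The effect on a rate is conditional. If transfusion need varies, the 2-unit rule can raise the chance rate of a 12-week transfusion-free interval by about 7 to 10 points with 2-unit episodes, or 2 to 4 with 1-unit episodes. With equal need it is close to zero. All of this rests on constant Poisson rates, assumed mixes and no drug effect. As this is a secondary endpoint, the change should be made, but the point does not threaten the primary analysis.

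**What to change.** - For the myelofibrosis arms, define baseline dependence in protocol 16.4.3 and SAP 4.3.1 by Table 15, footnote 6.
- Remove the baseline hemoglobin alternative from SAP 4.3.1.
- Keep the 2-unit, one-month rule for DIPSS-plus scoring in Appendix A only.
- For Arm G, use the MDS criteria in Section 11.2.
- In the same revision, align the SAP's independence rule with footnote 6: no red cell transfusion in a rolling 12-week interval, ending with hemoglobin of at least 85 g/L.
- State whether the proportion with its Clopper-Pearson interval is still estimated or replaced by the listing.

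**Cost.** Mostly wording. The denominator will probably, though not certainly, be smaller, because the sets are not nested; in the six-level mix 12–16% of patients meet only the 2-unit rule and 0–6% only the 6-unit rule. A smaller denominator widens the interval. Twelve weeks of transfusion history before enrollment are needed. Table 15 already requires that, but the test schedule states no look-back for the screening transfusion assessment, so its availability should be confirmed.
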